6.3 Retesting and rescreening

Retesting of laboratory assessments within the Screening Period is allowed as per the following:

- Study participants with isolated exclusionary laboratory assessments at Screening may have this laboratory assessment repeated once if, in the Investigator's opinion, the value is not reflective of the study participant's previous clinical and laboratory pattern. Retesting must be completed within the stated Screening Period. If the repeat values are within the acceptable ranges of the study and the study participant remains eligible during the Baseline Visit (Week 0), the study participant may be dosed.

Rescreening is only allowed after consultation with the Medical Monitor as per the following:

- Study participants who failed Screening (eg, due to transient out-of-range safety laboratory values or in the Investigator's judgment mild acute illness, eg, a cold) may be rescreened after complete recovery of the mild acute illness and/or normalization of the out-of-range safety laboratory values.
- Study participants who fulfilled all eligibility criteria but were registered as Screen failures due to suspension of enrollment as of 17 Jul 2013 are allowed to be rescreened.
- Rescreening might be allowed more than once but not in case of repeated occurrence of the same illness. All Screening assessments must be repeated as applicable in case of Rescreening. The maximum duration of the Rescreening Period is 28 days or 4 weeks. Rescreening must only be scheduled after an appropriate time period after the initial Screening Visit allowing for repetition of blood collection (depending on local requirements for maximum blood volumes; depending on study participant weight).
- All study participants who failed to be enrolled within the Screening Period of 28 days must be registered as Screen Failure in the interactive voice/web response system (IXRS). Study participants approved to be rescreened must be registered with a new study participant number.

6.4 Liver Chemistry Stopping Criteria

Participants with potential drug-induced liver injury (PDILI) must be assessed to determine if IMP must be discontinued. In addition, all concomitant medications and herbal supplements that are not medically necessary should be discontinued. The PDILI criteria below require immediate and permanent discontinuation of IMP:

- Participants with either of the following:
 - ALT or AST $\geq 5xULN$
 - ALT or AST $\geq 3xULN$ and coexisting total bilirubin $\geq 2xULN$

The PDILI criterion below requires immediate discontinuation of IMP:

- Participants with ALT or AST ≥ 3 xULN who exhibit temporally associated symptoms of hepatitis or hypersensitivity. Hepatitis symptoms include fatigue, nausea, vomiting, and right upper quadrant pain or tenderness. Hypersensitivity symptoms include fever (without clear alternative cause), rash, and eosinophilia (ie, $>5\%$).

The PDILI criterion below allows participants to continue on IMP at the discretion of the Investigator:

- Participants with ALT or AST ≥ 3 xULN (and ≥ 2 x baseline) and < 5 xULN, total bilirubin < 2 xULN, and no eosinophilia (ie, $\leq 5\%$), with no fever, rash, or symptoms of hepatitis (eg, fatigue, nausea, vomiting, right upper quadrant pain or tenderness).

Evaluation of PDILI must be initiated as described in Section 17.10. If participants are unable to comply with the applicable monitoring schedule, IMP must be discontinued immediately.

Investigators should attempt to obtain information on participants in the case of IMP discontinuation to complete the final evaluation. Participants with PDILI should not be withdrawn from the study until investigation and monitoring are complete. All results of these evaluations and observations, as well as the reason(s) for IMP discontinuation and participant withdrawal (if applicable), must be recorded in the source documents. The eCRF must document the primary reason for IMP discontinuation.

6.5 Withdrawal criteria

Study participants are free to withdraw from the study at any time, without prejudice to their continued care. Where possible, study participants discontinuing study medication should be encouraged to remain in the study.

A study participant may withdraw from the study at any time at his/her own request, or may be withdrawn at any time at the discretion of the investigator for safety, behavioral, compliance, or administrative reasons.

If the study participant withdraws consent for disclosure of future information, the sponsor may retain and continue to use any data collected before such a withdrawal of consent.

If a study participant withdraws from the study, he/she may request destruction of any samples taken and not tested, and the investigator must document this in the site study records.

See the Schedule of Activities for data to be collected at the time of study discontinuation and follow-up and for any further evaluations that need to be completed.

Study participants should be withdrawn from the study if any of the following events occur:

1. Study participant or legal representative withdraws his/her consent.
2. The sponsor or a regulatory agency requests withdrawal of the study participant.

Study participants must be permanently discontinued from study medication (but not necessarily from the study) if any of the following occurs:

1. Study participant/caregiver is noncompliant with the study procedures or medications in the opinion of the Investigator or Sponsor.
2. A study participant considered as having either a suspected new LTBI or who develops active TB or NTMB infection during the study (including but not limited to, conversion demonstrated by interferon-gamma release assay [IGRA] or other diagnostic means) must be immediately discontinued from IMP (refer to Section 10.7.9.8 for further details).
 - a) The study participant must be permanently withdrawn from the study if further examinations result in a diagnosis of active TB, NTMB infection, or if the study participant is diagnosed with LTBI. An Early Discontinuation visit must be scheduled as soon as possible, but not later than the next regular visit.

Any confirmed diagnosis or suspicion of a latent or active TB infection is a reportable event. Either type of infection must be reported as an adverse event of special interest (AESI) and must be captured on an AE report form, ticking the appropriate AESI and, if applicable, serious adverse event (SAE) field(s) on the form to clearly indicate the level of seriousness. A UCB TB follow-up form also must be completed. Confirmed active TB is an SAE and must be captured on an SAE report form and provided to the Sponsor in accordance with SAE reporting requirements. As with all SAEs, periodic follow-up reports should be completed as per protocol requirements until such time as the TB infection resolves.

3. Study participant is found to be persistently noncompliant (missing 2 or more consecutive scheduled CZP doses or missing 3 or more doses over a 12-month period), the Sponsor in conjunction with the Investigator will make a decision as to whether the study participant should be withdrawn from the study (see Section 7.7).

This rule does not apply when CZP is discontinued if the study participant is in CRM or if CZP is temporarily discontinued due to an AE. In the case of temporary discontinuation due to an AE, the Sponsor in conjunction with the Investigator will make a decision as to whether the study participant should be withdrawn from the study.
4. Study participant takes prohibited concomitant medications as defined in this protocol (see Section 7.8.3).

Study participants may be discontinued from study medication (but not necessarily from the study) if any of the following occurs, but may be restarted after consultation with the Medical Monitor:

1. Study participant develops an illness that would interfere with continued participation (eg, malignancies).
2. If there is a positive pregnancy test, study medication will be held. If there is confirmed pregnancy, study medication must be discontinued until end of the pregnancy. In case the study participant intends to breastfeed after a pregnancy study medication must be further discontinued until end of breastfeeding.

Investigators should attempt to obtain information on study participants, in the case of withdrawal or discontinuation. All results of these evaluations and observations, together with a narrative description of the reason(s) for removing the study participant, must be recorded in the source documents. For study participants considered as lost to follow-up the Investigator should make an effort (at least 1 phone call and 1 written message to the study participant), and document his/her effort (date and summary of the phone call and copy of the written message in the source documents) to complete the final evaluation. The CRF must document the primary reason for withdrawal or discontinuation.

Investigators should contact the Medical Monitor whenever possible to discuss the withdrawal of a study participant in advance.

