4.1.2 Safety variables

The primary safety variables will be the incidence of serious TEAEs and TEAEs leading to permanent withdrawal of IMP.

Adverse events will be solicited at every visit, recorded and coded according to Medical Dictionary for Regulatory Activities (MedDRA[®]) criteria.

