10.7.9.2 IGRA test conversion

Tuberculosis test conversion is defined as a positive or indeterminate (and confirmed indeterminate on repeat) IGRA result for the current test when previous IGRA test results were negative. All study participants with positive or indeterminate IGRA test results must immediately stop IMP administration. In case of an IGRA test conversion, the study participant must be considered as having either a suspected new latent or an active TB infection and be promptly referred to an appropriate specialist (eg, pulmonologist, infectious disease specialist) for further evaluation. Additional assessments (eg, blood tests or IGRA, chest X-rays, or other imaging) should be performed where medically relevant and documented. Such conversions should be reported as AEs as described in the protocol. The AE term would need to be updated with final diagnosis once available.

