10.7.9.3 Latent TB infection

In case the evaluation by the appropriate specialist diagnoses a new LTBI, the study participant must permanently stop IMP and be withdrawn from the study. A TB prophylactic therapy in accordance with applicable clinical guidelines might be initiated, if considered appropriate.

Once withdrawn from study treatment, study participants should return for the Early Discontinuation Visit and complete all early discontinuation assessments, and complete an Final Visit (12 weeks after the last dose of IMP). LTBI must be reported as an AE. Follow-up reports should be completed as per protocol requirement until such time as the LTBI resolves.

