During the conduct of the study, the TB assessment by IGRA can be repeated at the investigator's discretion. The TST test should not be repeated during the conduct of the study. The test results will be reported as positive, negative, or indeterminate and must be reviewed by an experienced TB specialist, radiologist, or a pulmonologist. If the assessment by IGRA is positive or indeterminate on retest, the study participant must undergo appropriate study-specified withdrawal procedures. The retest during Screening must be done during the protocol-defined Screening window.

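### The rules after an on-study positive or indeterminate IGRA conflict, mainly for participants whose evaluation ends without a TB diagnosis

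*Protocol*

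**What the plan says.** Section 6.5 has a list headed "Study participants must be permanently discontinued from study medication (but not necessarily from the study) if any of the following occurs". Item 2 of that list covers "A study participant considered as having either a suspected new LTBI or who develops active TB or NTMB infection during the study" and extends to "conversion demonstrated by interferon-gamma release assay [IGRA] or other diagnostic means) must be immediately discontinued from IMP". Sub-item 2a adds: "The study participant must be permanently withdrawn from the study if further examinations result in a diagnosis of active TB, NTMB infection", and names LTBI as well.

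Section 10.7.9.2 defines conversion as a positive result, or an indeterminate one confirmed on repeat, after earlier negative tests. Its next sentence is wider: "All study participants with positive or indeterminate IGRA test results must immediately stop IMP administration". A conversion is then to be treated as suspected latent or active TB and referred to a specialist. Section 10.7.9.3 takes over when that specialist "diagnoses a new LTBI, the study participant must permanently stop IMP and be withdrawn from the study".

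Section 10.7.9.5, on testing during the study, says: "If the assessment by IGRA is positive or indeterminate on retest, the study participant must undergo appropriate study-specified withdrawal procedures". Section 10.7.9.8.1 belongs to the TB management section that 6.5 cites for details. It says that participants who develop evidence of LTBI must stop study drug, be referred, and be withdrawn. Section 10.7.9.8.2, for children under 5 years, says only to stop and refer.

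Section 10.7.9(c) defines LTBI as a positive IGRA (or two indeterminate ones) with imaging negative for TB and no suggestive signs, symptoms or physical findings.

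On the endpoint, Section 4.1.2 states: "The primary safety variables will be the incidence of serious TEAEs and TEAEs leading to permanent withdrawal of IMP". Sections 10.1.6 and 10.7.9.2 make a conversion reportable as an adverse event. Table 5-1 schedules IGRA about once a year for everyone.

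**The concern.** A site holding a positive IGRA can find three different instructions. One stops study drug permanently but allows the participant to stay in the study. One stops drug while a specialist decides. One moves to withdrawal straight away. They differ on two separate questions: whether drug is stopped for good, and whether follow-up ends.

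The first question can reach a primary safety variable, because a conversion is itself an adverse event and the variable counts events that end study drug permanently. The second decides whether later safety, efficacy and (for those enrolled after Amendment 9) PK data exist for that child. A statistical analysis plan cannot resolve either, because both are settled by what the site does on the day.

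**Working it through.** The documents give no figure for this point, so the check is a comparison of the current text, followed by simple proportions for scale.

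**Step 1. Follow each possible situation through the sections.**

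| Situation | 6.5 item 2 | 10.7.9.2 and 10.7.9.3 | 10.7.9.5 | 10.7.9.8.1 |
|---|---|---|---|---|
| First indeterminate, retest pending | Not named | Drug stopped, though conversion is not yet met | No action before retest | Not named |
| First indeterminate, retest negative | Not named | Drug already stopped; no restart rule | No withdrawal | Not named |
| Positive or confirmed indeterminate, evaluation pending | Permanent stop by the heading; may stay in study | Stop and refer; permanence not stated | Withdrawal procedures | Withdrawal alongside referral, if the result is taken as evidence of LTBI |
| Same, specialist finds no LTBI, TB or NTMB infection | Permanently off drug; may stay in study | Condition for permanent stop and withdrawal not met; no restart rule | Withdrawal already triggered | Same as the row above |
| Diagnosis made | Off drug permanently and withdrawn | Off drug permanently and withdrawn | Withdrawn | Withdrawn |

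The last row agrees across all columns. The third and fourth rows do not. The first two rows show the mismatch inside 10.7.9.2, between the confirmed indeterminate that defines conversion and the unqualified indeterminate that stops drug.

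**Step 2. Is the word permanent in the 6.5 heading just loose drafting?** Section 6.4 separates immediate and permanent discontinuation from immediate discontinuation for liver events, so the protocol does use the word with intent. Section 6.5 also has a separate list of reasons after which drug may be restarted, and TB is not on it. Both support a literal reading of the heading. Section 10.7.9.3, however, attaches permanence to the specialist's diagnosis, which would be redundant if suspicion had already made the stop permanent.

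**Step 3. What is left for the specialist to decide?** Under 10.7.9(c), a positive IGRA with clear imaging and no symptoms is LTBI by definition. The fourth row is therefore populated only if the specialist may override that definition (for example after a further IGRA, which 10.7.9.2 allows), or if abnormal findings turn out to have another cause. The text does not say which.

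**Step 4. Scale.** Section 13.8 gives 78 participants on the original regimen and 78 planned on the reduced one, then 30 more on the original regimen: 78 + 78 = 156; 156 + 30 = 186; original-regimen starters 78 + 30 = 108. If k participants are classified differently, the incidence shifts by k/N:

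| k | N = 186 | N = 108 (original) | N = 78 (reduced) |
|---|---|---|---|
| 1 | 0.54 points | 0.93 points | 1.28 points |
| 2 | 1.08 points | 1.85 points | 2.56 points |
| 5 | 2.69 points | 4.63 points | 6.41 points |

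The values of k are illustrations, not estimates; the protocol gives no conversion rate. The Summary mentions 163 participants in the first interim, so the final denominator could be nearer 163 + 30 = 193, and 1/193 = 0.52 points. That changes nothing of substance.

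**The case against.** The strongest defence is that the sections mostly share one structure: stop on suspicion, leave the study on diagnosis. On that view, 10.7.9.5 refers to withdrawal procedures specified elsewhere and creates no third rule. The defence has force for 10.7.9.5. It fails for 10.7.9.8.1, which requires withdrawal alongside referral with no diagnosis condition, and it does not explain why 6.5 puts mere suspicion under a permanent-stop heading.

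It can also be said that resumption of drug is only an inference, because no TB section contains a restart rule. That is correct. The text neither permits nor forbids restart for a participant the specialist clears, and that gap is part of the problem.

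Three stronger readings are tempting and are not supported:

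- A reader might infer that the primary safety variable generally depends on which section a site follows. It does not. Diagnosed cases are permanently off drug everywhere, and most positive results with clear imaging meet the LTBI definition outright. A single unconfirmed indeterminate result is not a reportable conversion under 10.1.6, so it does not clearly enter the variable at all. Withdrawal from the study rather than from drug changes follow-up, not the event count.
- A reader might multiply the yearly tests by a positivity rate and call every positive result reclassified. That counts the very group in which the sections converge.
- A reader might infer that these stops would be indistinguishable from tolerability withdrawals. The adverse event term is updated to the final diagnosis, TB events carry their own follow-up form, and the CRF records the primary reason for discontinuation, so they can be told apart.

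**Conclusion.** The contradiction is in the current text and should be corrected. It is explicit on study withdrawal (test result or evidence in one place, diagnosis in another) and on the trigger for an indeterminate result. On permanent versus provisional stopping of drug it is partly by implication.

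Its reach is narrow. It affects mainly participants with a positive or indeterminate IGRA whose evaluation does not end in LTBI, TB or NTMB infection. The effect on the primary safety variable is narrower still, since it needs a conversion reported as an adverse event in a participant who is then cleared. How many there will be cannot be derived from the protocol; the number is probably small. The per-participant shifts of 0.54 and 1.28 points rest on the planned 186 and 78. No view is taken on which clinical rule is right.

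**What to change.** Reconcile Section 6.5 item 2 and Sections 10.7.9(c), 10.7.9.2, 10.7.9.3, 10.7.9.5 and 10.7.9.8.1 into one sequence with five steps: first indeterminate, confirmed indeterminate, positive, specialist-confirmed, specialist-excluded. At each step, state whether study drug is interrupted or permanently stopped and whether the participant stays in the study. The under-5 text in 10.7.9.8.2 should point to the same sequence. The sponsor's TB experts should choose the clinical rule.

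Add one sentence saying when an adverse event arising from an IGRA result counts as leading to permanent withdrawal of study drug, so that every site and the analysis use the same moment. The same edit can correct Section 10.7.9, which cites the TB withdrawal criterion as Section 6.4, now the liver stopping criteria; it stands in 6.5.

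The cost is amendment wording in six places plus that sentence, with no added visits or tests. Treatment is open-ended and testing recurs yearly, so the change still helps participants already enrolled.

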7 STUDY TREATMENTS

7.1 Description of IMP

Supplies of CZP will be provided by UCB as a CZP 200mg/mL solution for single sc injection, in a single use PFS for sc injection (administered in accordance with [Table 7-1](#)). Each PFS contains an extractable volume of 0.25mL, 0.5mL, or 1mL of CZP solution.

The IMP will be supplied under the responsibility of UCB. The frequency at which the IMP will be supplied to each individual center will be adapted based on the recruitment capacity of that center, availability, and expiry date of the IMP. Study medication supplies will be managed by the IXRS in order to ensure all sites have sufficient quantities of study medication available.

7.2 Treatments to be administered

Throughout the study, CZP dosing is fixed dose based on weight and given Q2W, with the exception of the lowest weight group on the reduced CZP regimen who will receive the maintenance dose Q4W. The loading dose, maintenance dose, and range of exposures in each weight category for both the original and reduced CZP regimens are presented in [Table 7-1](#). Study participants start with 3 loading doses of CZP at Weeks 0, 2, and 4 followed by a maintenance dose for the duration of the study. After Week 4 (Visit 5), home-based CZP administration by the study participant or parent/caregiver will be permitted between scheduled study visits.

A study participant's dosing category will only be changed after the confirmation of a weight change by the Investigator **at a scheduled clinic visit**.

The study participant will receive the dose of the next weight category once their weight crosses the 40kg/88lb boundary or crosses the 20kg/44lb boundary at a scheduled clinic visit. The study participant will continue on the dose of the new weight category regardless of potential decrease of the weight below the boundary. In case of significant weight fluctuations the Investigator should contact the Medical Monitor to discuss and confirm potential change in dosing if medically advised or discontinuation of treatment (eg, if related to AE).

The injection should be administered at either the lateral abdominal wall or upper outer thigh. Treatment of the injection site with an anesthetic cream prior to dosing is permitted.

Table 7-1 Dosing administration of CZP^a

| Weight range | Loading dose – Weeks 0, 2, and 4 (mg/kg dose range) IMP Description | Maintenance – Week 6 and onwards (mg/kg dose range) IMP Description |
|------------------------------|---|---|
| Original CZP regimen | | |
| 10 to <20kg (22 to <44lb) | 100mg Q2W (5-10mg/kg) 1 x 0.5mL inj | 50mg Q2W (2.5-5mg/kg) 1 x 0.25 mL inj |
| 20 to <40kg (44 to <88lb) | 200mg Q2W (5-10mg/kg) 1 x 1mL inj | 100mg Q2W (2.5-5mg/kg) 1 x 0.5mL inj |
| ≥40kg (≥88lb) | 400mg Q2W (<10mg/kg) 2 x 1mL inj | 200mg Q2W (<5mg/kg) 1 x 1mL inj |
| Reduced CZP regimen | | |
| 10 to <20kg (22 to <44lb) | 50mg Q2W (2.5-5mg/kg) 1 x 0.25mL inj | 50mg Q4W (2.5-5mg/kg) 1 x 0.25mL inj |
| 20 to <40kg (44 to <88lb) | 100mg Q2W (2.5-5mg/kg) 1 x 0.5mL inj | 50mg Q2W (1.25-2.5mg/kg) 1 x 0.25mL inj |
| ≥40kg (≥88lb) | 200mg Q2W (<5mg/kg) 1 x 1mL inj | 100mg Q2W (<2.5mg/kg) 1 x 0.5mL inj |

CZP=certolizumab pegol; inj=injection; Q2W=every 2 weeks; Q4W=every 4 weeks

Note: A study participant should change dosing category during the course of the study if their weight crosses the 40kg/88lb boundary or crosses the 20kg/44lb boundary.

^a Note that the original CZP regimen describes the dosing administration of CZP prior to the implementation of Protocol Amendments 4 and 5 and for study participants enrolled following the implementation of Protocol Amendment 9. The reduced CZP regimen describes the dosing administration of CZP after implementation of Protocol Amendments 4 and 5. Refer to Section 7.2.1 for the procedure to be taken for study participants who are undergoing a dose change.

Site staff will administer the study participant's injection at Week 0 to demonstrate the correct injection technique. At Weeks 2 and 4, study participants/caregivers may administer the study medication under the supervision of the site staff to ensure that the study medication is being properly and safely injected. Once study participants/caregivers have been trained, the study medication may be administered at home. Prior to CZP administration at home, study participants/caregivers will be trained by the site staff and provided written instructions on the fixed dose for injection and the correct sc injection technique including 0.25mL, 0.5mL, and 1mL injections, as appropriate. If administered at home, the study participant/caregiver is requested to document the container number, date, and time point of

administration of study medication and return this documentation together with any used/unused or partially used containers at the next scheduled clinic visit. Study participants who are unable to self-administer the study treatment or those without a family member/friend/caregiver who can help, will not be withdrawn from the study but may continue to visit the site for study treatment administration between regular scheduled visits. In addition, if needed, home dosing can be performed by qualified health care professionals according to the written instructions for the correct sc injection technique provided by the site staff. Study participants will have the option to either switch to home-based CZP injection or switch back to administration at the study site at anytime during the study.

The method of injection (ie, qualified site personnel-injection at study site; injection by the study participant/caregiver or qualified health care professional at the study site or at home) and the site of injection (abdomen, thigh) will be recorded in the CRF at each visit.

Study participants achieving clinical remission on medication (CRM), ie, after 6 months of continuous CID, may discontinue CZP treatment at the Investigator's discretion following consultation with the Sponsor to confirm remission status. Study participants who have discontinued CZP due to achieving CRM will be allowed to remain in the study and continue with scheduled study visits. Study participants not maintaining persistent CID following achievement of CRM will be allowed to resume CZP treatment at any time at the Investigator's discretion and consultation with the Sponsor. If a study participant is on concomitant MTX treatment, the Investigator may decide to decrease and ultimately discontinue the MTX dose after complete discontinuation of CZP. Study participants not maintaining persistent CID following achievement of CRM and resuming treatment will restart the fixed-dose CZP dosing based on their current weight with 3 loading doses of CZP administered Q2W over 6 weeks, followed by a maintenance dose administered Q2W, or Q4W for the lowest weight group on the reduced CZP regimen for the duration of the study (see [Table 7-1](#)).

